**Abstract:**

Dry eye (DE) is a common complaint of millions of people worldwide with a significant impact on quality of life. For decades, this condition has presented a challenge to eye care professionals as conventional therapies are often ineffective. Recently, scleral lenses have demonstrated to be a promising therapeutic and vision rehabilitative option for dry eye sufferers. Nonetheless, despite the benefits of scleral lenses for dry eye patients, inadequate wettability of scleral lenses with subsequent diminished comfort and visual clarity remains a concern for scleral lens wearers with dry eye.

Tangible Hydra-PEG™ (Tangible Science LLC, Menlo Park, CA, USA) is a novel coating technology designed to improve lens wettability, deposit resistance and tear film breakup time, ultimately enhancing contact lens comfort. While studies have shown that Tangible Hydra-Peg technology can improve contact lens discomfort (CLD) in soft contact lens and gas permeable lens wearers, to our knowledge, no clinical research investigation has examined the benefits of this new coating on scleral lens wear in dry eye sufferers. As such, the aim of this study is to compare the CLD and DE symptoms of dry eye scleral lens wearers between Tangible Hydra-Peg treated scleral lens wear and untreated scleral lens wear. CLD and DE signs will also be assessed to corroborate our findings.

This will be the first randomized double masked cross-over study to examine CLD and DE symptoms of Tangible Hydra-Peg treated scleral lens wear as compared to untreated scleral lens wear in the dry eye patient population. Tangible Hydra-Peg treated scleral lenses can potentially minimize CLD and DE symptoms, ultimately improving outcomes for patients coping with dry eye disease. This study will provide new information about this innovative technology and help practitioners envisage rehabilitative options which will best optimize the quality of life of this important patient population.

## **Specific Aims:**

1. The primary goal of this study is to compare the CLD and DE symptoms of moderate to severe DE subjects between 30 days of Tangible Hydra-Peg treated scleral lens wear and 30 days of untreated scleral lens wear.  
Hypothesis: CLD and DE symptoms will be significantly better after 30 days of Hydra-Peg treated scleral lens wear as compared to 30 days of untreated scleral lens wear.
2. The secondary goal of this study is compare the CLD and DE signs of moderate to severe DE subjects between 30 days of Tangible Hydra-Peg treated scleral lens wear and 30 days of untreated scleral lens wear in DE subjects. As DE can impact vision quality and Hydra-Peg may impact contact lens wearing times, as a subanalysis, we will also examine contact lens wearing times and quality of vision such as frequency of foggy vision between treated and untreated scleral lens wear.

Hypothesis: CLD and DE signs will be significantly better after 30 days of Hydra-Peg treated scleral lens wear as compared to 30 days of untreated scleral lens wear. Frequency of foggy vision and contact lens wearing time will be significantly better after 30 days of Hydra-Peg treated scleral lens wear as compared to 30 days of untreated scleral lens wear.

## **Methods:**

### Participant Recruitment

In a multi-center randomized double-masked cross-over study, 30 scleral lens wearers with CLD and moderate to severe DE shall be recruited for a non-significant risk 1-month study. Participants will be enrolled at three geographically diverse academic site locations across North America (Fort Lauderdale, FL, Chicago, Illinois, and Sacramento, CA). The participants will be randomly selected from those exhibiting CLD and moderate to severe symptomatic dryness as determined by the validated and commonly used Ocular Surface Disease Index (OSDI) dry eye questionnaire (Appendix A) and the validated Contact Lens Dry Eye Questionnaire-8 (CLDEQ-8) (Appendix B). These symptom surveys are recommended to be included in a clinical study assessing DE and CLD by expert researchers of the International Dry Eye Workshop and the International Workshop on Contact Lens Discomfort respectively. The participants will be 18 to 70 years of age and have the presence of reduced tear film break up time (TBUT), a sign of DE and CLD.

A participant will be defined as a scleral lens wearer if he or she reports wearing his or her lenses at least 8 hours per day for at least 5 days per week and have had their habitual lenses no longer than 1 year. Due to the widely varying parameters of scleral lenses and lens diameter having an impact on comfort, in this study scleral lens wear will be defined as 15.0 mm to 19.00 mm inclusive. All participants will be required to remain in primarily the same scleral lens

parameters including material throughout the study, except for the change in lens coating. Except for the wash-out periods, all subjects will be required to continue with the same supportive dry eye therapy and use hydrogen peroxide for lens care throughout the study.

Participants with the following will be excluded from this study: disorders that affect sensitivity (herpetic disease, severe diabetes mellitus), anatomic variations of the conjunctiva that can impair proper scleral lens fitting, pregnancy, and significant visual impairment that could confound the results of the study which, for the purposes of this study, will be defined as best corrected Snellen visual acuity worse than 20/30 in either eye or any other ocular pathology (e.g. glaucoma, macular degeneration, keratoconus) other than DE, which may significantly impact visual function.

### Experimental Design

30 subjects with symptomatic moderate to severe dry eye and symptoms of CLD will complete a double-masked cross-over study. The participants will be randomly chosen to wear their habitual untreated scleral lenses or Hydra-Peg treated scleral lenses first for 30 days. Half of the participants (15) will be randomly chosen to wear the Hydra-Peg treated scleral lenses first for 30 days, and the other half of the participants (15) will be chosen to wear their habitual untreated scleral lenses for 30 days first. One week wash-out periods with no lens wear will be placed before and between the 30-day test periods. The OSDI, CLDEQ-8, a battery of dry eye diagnostic tests, and tests which will assess the impact of contact lenses on the ocular surface will be administered from 3:00 to 5:00 pm at baseline, after the first test period, and after the cross-over. Contact lens wearing time and questions related to quality of vision will also be collected at baseline, after the first test period, and after the cross-over.

The battery of clinical dry eye sensitive tests will include, TBUT of the ocular surface, and ocular surface staining. TBUT over the surface of the scleral lenses, lid wiper epitheliopathy (LWE), and contact lens-related papillary conjunctivitis we will also be examined as they these factors may change with alteration of a contact lens surface.

The study will be double-masked. Lens pairs will be supplied in identical cases, differing only by code mark unknown to the tester. Only one lens pair during the respective test period (treated or untreated) will be given to each participant. The general study schedule following recruitment is described below.

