## General Study Schedule

### To obtained informed consent

Day 1	Screening  1) Informed Consent, HIPAA authorization 2) OSDI and CLDEQ-8  3) Assessment of TBUT
Days 1-8 (1 week)	Wash-out period
Days 9	Baseline Testing (1) OSDI, CLDEQ-8, additional questions (skip questions 3 and 5) (2) Battery of Clinical tests (3) Randomization of lenses
Days 9-39 (30 days)	Test Period 1 Wear of treated or untreated CL
Day 40	Post CL Wear Testing (1) OSDI, CLDEQ-8, additional questions (2) Battery of Clinical Tests
Day 40-47 (1 week)	1 week Wash-out Period
Days 48-78 (30 days)	Test Period 2 Wear of treated or untreated CL
Day 79	Post CL Wear Testing (1) OSDI, CLDEQ-8, additional questions (2) Battery of Clinical Tests

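### The Experimental Design section does not consistently define the untreated control lens; if it is the participant's own habitual lens, coating is confounded with lens pair and familiarity, and participant masking is not secured

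*Combined protocol and SAP*

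**What the plan says.** Two sentences in Experimental Design name the untreated condition as the lens the participant already owns. The first covers both sequences: "The participants will be randomly chosen to wear their habitual untreated scleral lenses or Hydra-Peg treated scleral lenses first for 30 days". The second covers the control-first sequence: "the other half of the participants (15) will be chosen to wear their habitual untreated scleral lenses for 30 days first".

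The masking paragraph of the same section reads differently: "Lens pairs will be supplied in identical cases, differing only by code mark unknown to the tester", followed by "Only one lens pair during the respective test period (treated or untreated) will be given to each participant".

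Three other places bear on the control lens without settling its source:

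- Participant Recruitment requires that participants "have had their habitual lenses no longer than 1 year", and asks them to stay in primarily the same "parameters including material throughout the study, except for the change in lens coating".
- The General Study Schedule says only "Wear of treated or untreated CL" for each test period and places randomisation of lenses on Day 9.
- Specific Aims compares treated with untreated wear and does not say where the untreated lens comes from.

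The study is declared double-masked in both Participant Recruitment and Experimental Design. The primary aim concerns symptoms, measured by the OSDI and CLDEQ-8, both completed by the participant.

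**The concern.** The trial asks what the coating does. That question is answered cleanly only if the two lenses a participant wears differ in coating and in nothing else that affects comfort. A habitual lens differs in other ways: it is a different physical pair, the wearer knows it, and it may have months of wear on it. The Abstract lists deposit resistance and wettability among the routes by which the coating should improve comfort, so the surface state of a worn control lens could act through the same route.

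Masking is also at stake. The primary outcomes are self-reported, so it is the participant's masking that protects them. The text says the code is unknown to the tester and is silent on the participant. Nothing explains how a wearer would fail to recognise their own lens.

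If the habitual lens is the control, a difference in symptoms, or the lack of one, could not be attributed to the coating, and no later analysis could separate the two.

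**Working it through.** **1. The plan's own figure.** The allocation is 15 treated first plus 15 untreated first: 15 + 15 = 30, which agrees with the stated total. The plan gives no alpha, effect size, SD or power, so the 30 cannot be checked further.

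**2. Can the statements be read together?** There are three candidate readings.

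- *Habitual pair collected and returned in a coded case.* This reconciles the wording, but it confirms that a familiar, possibly worn lens is the control. The schedule lists no visit at which the lens is collected and coded.
- *Habitual pair itself coated for the treated period.* The 15 treated-first participants would then need the same pair back in an untreated state after a one-week wash-out. No such step is described, so the treated lens has to be a separate pair.
- *Two matched study-made pairs.* This fits the masking paragraph and the same-parameters rule, but then the word habitual in both allocation sentences is wrong.

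**3. Does the cross-over remove a lens-pair effect?** Let tau be the coating effect, b the effect of everything else that differs between the two pairs (pair, familiarity, wear), and p the period effect (period 2 minus period 1). Carry-over is ignored. The treated-minus-untreated difference is:

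- treated first: tau + b - p
- untreated first: tau + b + p
- average over 15 and 15: tau + b

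The period effect cancels and b does not. The paired t-test or Wilcoxon test in Statistical Analysis therefore tests tau + b. With two matched unworn pairs, the part of b due to age, prior wear and familiarity is zero by design.

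**4. How different could the lens histories be?** Eligibility requires "wearing his or her lenses at least 8 hours per day for at least 5 days per week", so at least 8 x 5 = 40 h per week, with ownership of up to 1 year.

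| Ownership before study | Earlier wear at the minimum rate |
|---|---|
| 3 months | about 521 h |
| 6 months | about 1,043 h |
| 12 months | 40 x 52.14 = about 2,086 h |

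One 30-day test period at the same rate is 40 x 30/7 = about 171 h, and 2,086/171 is about 12. The plan sets no wearing hours for the test periods, so applying the eligibility minimum there is an assumption, and 12 months is the longest ownership allowed. Hours of wear do not convert to symptom points. The table shows a contrast in history, not a bias.

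**5. Illustration of sensitivity.** n = 30 is from the plan. The two-sided alpha of 0.05 and every value of b are assumed. Units are SDs of the paired differences.

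- Critical t on 29 df is 2.045, so the smallest significant mean difference is 2.045/sqrt(30) = 0.373 SD.
- With tau = 0, the noncentral t probability of declaring benefit for the treated lens is 2.5% at b = 0, 7.6% at b = 0.1 and 26.2% at b = 0.25.
- With tau = 0.529 SD (power 80% at b = 0), power is 62% at b = -0.1 and 31% at b = -0.25.

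**The case against.** The best defence is that this is an ambiguity and not a demonstrated flaw. Habitual may be shorthand for the habitual lens design without coating, which fits the same-parameters rule, and the masking paragraph describes what a matched-pair trial would do. If so, there is no built-in confounding. That stands, and it makes the confounding conditional. It does not remove the need for an edit, because a site following the allocation sentences as written would dispense the participant's own lens.

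Four stronger readings are tempting, and the documents do not support them.

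- *That several sections contradict one another.* The conflict lies inside Experimental Design. Participant Recruitment and the schedule are compatible with either reading and simply fail to resolve it.
- *That a new lens is certainly compared with a worn one.* A separate treated pair follows from the treated-first sequence, but the age and condition of that pair are not stated. Confounding with prior wear holds only if it is newer.
- *That participants will know the code.* The text says the tester does not know it. Silence about the participant is not a statement that the participant does.
- *That the illustrative error rates measure the problem.* They rest on assumed bias sizes and carry no weight for severity.

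The 1-year cap on ownership also counts in the plan's favour, since it limits lens age, though it does not equalise it. The direction of bias is open as well: a fresher surface could favour the treated lens, and familiarity could favour the habitual one.

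**Conclusion.** The untreated control lens is not consistently defined within Experimental Design, and no other section settles it. Confidence in that is high.

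If the allocation sentences are followed as written, coating is confounded with lens pair and familiarity, and with prior wear if the treated pair is newer. Randomised order and the paired test do not remove this, and the double-masked label is not secured for the OSDI and CLDEQ-8. This part is conditional on that reading. The size and direction of the bias cannot be found from the documents; all that can be bounded is ownership of the control lens, from 0 to 12 months. If matched, unworn study pairs are meant, this confounding does not arise.

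The point concerns the comparator of the primary aim and cannot be repaired once data are collected, so it should be resolved before enrolment.

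**What to change.** In Experimental Design:

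1. Replace the habitual untreated lens, in both allocation sentences, with a study-supplied untreated pair.
2. State that the treated and untreated pairs are both unworn at dispensing and made to the same parameters and material. Specifying only the untreated pair would leave the age of the treated pair open.
3. State that the code is unknown to both participant and tester.

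The cost is about one untreated pair per participant, so about 30, plus any remakes or replacement participants. It is nothing beyond wording if such pairs were already planned. The price of a pair is not in the documents. The trial would no longer estimate the effect of switching from the lens currently worn, but that is not its stated aim.

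If the sponsor keeps the habitual lens as control, limit the conclusion to treated study lens versus habitual lens, do not claim participant masking for the symptom outcomes, record the age of both pairs, and name in the General Study Schedule the visit at which the habitual lens is collected and coded. That costs wording and a few recorded items, and it leaves the confounding in place.

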## Statistical Analysis

The key values used for analysis in this study will be differences in CLD and DE symptoms following scleral lens wear with Tangible Hydra-Peg and that found after untreated scleral lens wear. In addition, we will examine differences in CLD and DE signs between Tangible Hydra-Peg scleral lens wear and untreated scleral lens wear. Preliminary data analyses will include inspection for kurtosis and skewness of each distribution and test for normality, using the Shapiro-Wilk test. Normal distributions will be analyzed using a paired t-test. Non-normal distributions will be analyzed with the Wilcoxon Signed Ranked test.

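### The planned paired t-test ignores lens order and site, so any change between the two test visits widens the error of the lens comparison; balance of order within sites is also unspecified (minor loss of precision, no bias)

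*Combined protocol and SAP*

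**What the plan says.** The Experimental Design section describes a two-period cross-over: "30 subjects with symptomatic moderate to severe dry eye and symptoms of CLD will complete a double-masked cross-over study". It gives one constraint on allocation: "Half of the participants (15) will be randomly chosen to wear the Hydra-Peg treated scleral lenses first for 30 days". The remaining 15 start with their untreated lenses. The General Study Schedule adds only the entry "Randomization of lenses" at Day 9. Neither place describes how the list is made, or mentions stratification or blocking.

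The Participant Recruitment section says "Participants will be enrolled at three geographically diverse academic site locations across North America". It gives no number per site and no enrolment calendar.

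In the General Study Schedule, "Post CL Wear Testing" falls on Day 40 and Day 79 of each participant's own schedule, so the two outcome measurements are 79 − 40 = 39 days apart.

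The Statistical Analysis section says "Normal distributions will be analyzed using a paired t-test", with the Wilcoxon signed-rank test for non-normal data. Neither analysis has a term for period, order or site. No alpha, effect size, SD or power is stated.

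**The concern.** In a two-period cross-over, each participant's lens difference also contains whatever else changed between the two visits. The sign of that change depends on which lens came first. A paired t-test treats it as noise between participants.

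There are two consequences. First, a change shared by everyone cancels from the mean because the orders are 15/15, but it still inflates the SD, so the reported standard error is too wide. Second, a change that differs by site does not fully cancel from the mean unless order is balanced within each site, so part of it enters the lens estimate as random error.

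What is at stake is power, in a trial fixed at 30 participants with no stated calculation showing that it has precision to spare.

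**Working it through.** **Inputs.** From the documents: 30 participants, 15/15 by order, three sites, outcomes at Day 40 and Day 79, paired t-test. Assumed, because not stated: 10 participants per site; two-sided alpha 0.05; SD of the paired difference 1 when nothing changes over time; true lens effect 0.53 SD, chosen because it gives about 80% power with 30 pairs. The plan has no power figure to reproduce; 15 + 15 = 30 is consistent.

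**Model.** d = τ + s·π_site + e. Here d is treated minus untreated, s = +1 if untreated came first and −1 if treated came first, π_site is the Day 40 to Day 79 change at that site, and SD(e) = 1.

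**Step 1: balance within site, if the only restriction is 15/15 overall.** The probability of a, b and c treated-first participants at the three sites is C(10,a)·C(10,b)·C(10,c)/C(30,15).
- All sites 5/5: 252³/155,117,520 = 10.3%.
- At least one site 7/3 or worse: 46.7%. At least one 8/2 or worse: 12.2%.
- With other site sizes, the chance that some site's two orders differ by 4 or more is 45% (12/12/6), 31% (15/10/5) or 27% (20/5/5).

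**Step 2: common change of 0.5 SD.** The estimate is unaffected, since the s values sum to zero. The expected sample variance becomes 1 + 0.5² × 30/29 = 1.259, so SD = 1.122 and the reported SE is 1.122/√30 = 0.205, against a true SE of 1/√30 = 0.183. Significance needs a mean above about 2.045 × 0.205 = 0.419. Then (0.53 − 0.419)/0.183 = 0.61, which gives power of about 73%. Simulated type I error is about 3%, so the test is conservative.

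**Step 3: changes of +s, 0, −s at the three sites, no blocking.** The error added to the mean is (1/30)·Σ π_site·(order imbalance at that site), with expectation zero. The variance of the estimate rises by the factor 1 + s² × (2/3) × (30/29):
- s = 0.3: 1.06
- s = 0.6: 1.25
- s = 0.9: 1.56

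The paired SD rises to match, so type I error stays near 5%.

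**Step 4: power under each design and analysis.** Simulated, at least 8,000 runs per cell, Monte Carlo error about 0.5 point or less:

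| Change between visits | Paired t, unblocked | Paired t, 5/5 per site | Order within site, unblocked | Order within site, 5/5 per site |
|---|---|---|---|---|
| None | 80% | 80% | 77% | 80% |
| ±0.3 SD by site | 78% | 78–79% | 77% | 80% |
| ±0.6 SD by site | 71% | 73% | 77% | 80% |
| ±0.9 SD by site | 62% | 64% | 77% | 80% |
| Common 0.5 SD | 73% | 73% | 77% | 80% |

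A single order term common to all sites restores 80% in the last row, but leaves about 78%, 71% and 61% in the three site-specific rows.

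Blocking alone recovers only about 0–3 points. It makes the estimate more precise, but the paired t-test still reports an SE based on the inflated SD. Most of the recovery comes from the analysis. Blocking then removes the roughly 3-point cost of fitting order within site on an unblocked list.

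**The case against.** The strongest case against is that the harm rests on a change the documents never describe. They give no season, climate, staffing change or size of drift. The sites are called geographically diverse and nothing more. Days 40 and 79 count from each participant's own start, so a seasonal change is shared within a site only if its participants enrol at about the same time, and no calendar is given. A change of examiner would bear mainly on the secondary signs, because the primary symptoms come from questionnaires. The largest losses need opposite site changes of 0.6–0.9 SD, larger than the assumed lens effect. All of this stands, and it limits the priority.

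Three stronger readings are tempting and are not supported:
- **That order is not balanced within sites.** The documents are silent on how the list is made, and 15/15 overall is compatible with 5/5 at each site. The imbalance figures hold only if allocation is otherwise unrestricted.
- **That the lens result would be biased, or driven by one site.** Under random order the estimate is unbiased, and type I error is near or below 5% in every case run.
- **That missing site blocks are the main fault.** Blocking with the paired t-test retained changes little.

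What the objection does not remove is that the planned test discards known information on order. Even a change common to all sites costs power, and using that information costs almost nothing.

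**Conclusion.** The point holds as a minor precision issue, located mainly in the Statistical Analysis section. The planned test leaves any change between the two visits in its error term, and the plan does not say whether lens order is balanced by site.

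On the stated assumptions, the loss is about 7 points of power for a common 0.5 SD change. For opposite site changes of 0.3, 0.6 and 0.9 SD it is about 2, 9 and 18 points. At 0.3 SD or less the loss is small. Whether any such change will occur cannot be judged from the documents. The power figures are for the paired t-test; the Wilcoxon alternative has the same omission but was not quantified.

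**What to change.** **Statistical Analysis (main change).** Replace the paired t-test with a regression of each participant's treated-minus-untreated difference on lens order, coded +1/−1, with a separate order coefficient for each site and one common intercept. The intercept is the lens effect averaged over the two orders; report it with its confidence interval. If a rank method is kept for non-normal data, it should also use order: compare the Day 79 minus Day 40 differences between the two order groups, stratified by site.

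**Experimental Design (supporting change).** State how the list is produced, and randomise order in permuted blocks (random sizes 2 and 4) separately at each site, prepared centrally. This must be set before the first participant is randomised. If blocking by site is not possible, a single order term common to all sites still deals with a common change at almost no cost.

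**Cost.** A different list and one model line. The model uses up to 3 residual degrees of freedom (critical t from 2.045 to 2.056), which costs under about 1 point of power if nothing changes between visits. The overall split could end at 14/16 if a site stops mid-block.

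### Does printing Day 40 as both the post-wear test day and the first day of the no-lens wash-out rule out the lens-surface measurement?

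*Combined protocol and SAP*

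**What the plan says.** Experimental Design sets the rule for the lens-free weeks: "One week wash-out periods with no lens wear will be placed before and between the 30-day test periods". It places the questionnaires and clinical tests at three visits, which "will be administered from 3:00 to 5:00 pm at baseline, after the first test period, and after the cross-over". The dry eye battery covers "TBUT of the ocular surface, and ocular surface staining". The same section adds "TBUT over the surface of the scleral lenses, lid wiper epitheliopathy (LWE), and contact lens-related papillary conjunctivitis" as further signs, because they may respond to a changed lens surface. It also collects contact lens wearing time at all three visits.

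The General Study Schedule gives the days:

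- Day 1, screening; Days 1-8, wash-out.
- Day 9, baseline testing and randomization; Days 9-39, Test Period 1.
- Day 40, "Post CL Wear Testing"; Days 40-47, wash-out.
- Days 48-78, Test Period 2; Day 79, the same post-wear testing again.

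Neither section says whether participants arrive at Days 40 and 79 wearing lenses, how long the lenses have been on, or in what order lens-surface and ocular-surface tests are done. Statistical Analysis compares treated with untreated wear within participants: "Normal distributions will be analyzed using a paired t-test", with the Wilcoxon signed-rank test otherwise. It uses no baseline value.

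**The concern.** Taken word for word, Day 40 belongs to a week without lenses, yet it is also the day on which TBUT over the lens surface is due. Day 79 belongs to no wash-out. On that reading, the first-period value of this sign could not be obtained, and every participant would lose one half of the treated/untreated pair.

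The sign is not trivial. The Abstract describes the coating as "designed to improve lens wettability, deposit resistance and tear film breakup time", so lens-surface TBUT lies closest to the claimed mechanism.

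A milder version also deserves a check. If lenses were on at one post-wear visit and off at the other, or if the three sites handled this differently, the ocular-surface signs would be read under unlike conditions. The paired test has no period term to absorb a difference between visits.

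**Working it through.** **1. Reproduce the printed durations.** Inputs are the day ranges in the General Study Schedule.

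| Row | Printed label | End minus start | Inclusive count |
|---|---|---|---|
| Days 1-8 | 1 week | 8 − 1 = 7 | 8 |
| Days 9-39 | 30 days | 39 − 9 = 30 | 31 |
| Days 40-47 | 1 week | 47 − 40 = 7 | 8 |
| Days 48-78 | 30 days | 78 − 48 = 30 | 31 |

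Elapsed-day counting matches all four labels; inclusive counting matches none. The table therefore treats the first printed day of a period as its starting point, not as a full day within it.

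**2. Is Day 40 an exception?** Three visits are followed by a period (Days 1, 9 and 40), and all three share their day with that period. In each case the visit row is printed first. For two of them the order is forced: consent is taken at the Day 1 visit, so the wash-out cannot come before it, and lenses are randomized at the Day 9 visit, so test wear cannot come before it. Day 40 has the same layout. Day 79 is unshared only because nothing follows it.

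**3. Does the wash-out keep its length if it starts after the Day 40 visit?** Days 41 to 47 inclusive: 47 − 41 + 1 = 7 full lens-free days, the stated week.

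**4. Are the two post-wear visits alike on paper?** Gap from last printed wear day to test: 40 − 39 = 1 and 79 − 78 = 1. Gap from first printed wear day to test: 40 − 9 = 31 and 79 − 48 = 31. Label, content and clock window are the same. Nothing in the schedule gives the visits different lens status unless the Day 40 wash-out is taken to start before the visit listed above it.

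**5. Differences between sites.** Suppose a site's practice adds a constant s to a sign at both visits. The paired difference is (τ + s) − s = τ, where τ is the treatment effect. Under this additive assumption, and with each participant staying at one site, a consistent site practice cancels.

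**6. What if lens status did differ between Days 40 and 79?** Let d be the resulting shift, in SDs of the paired difference. Treated minus untreated is τ − d in one sequence and τ + d in the other.

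- Bias in size: d × |n₁ − n₂| / (n₁ + n₂). At the planned 15/15 it is 0. At an assumed 15/12 among completers it is 3/27 = 0.11 d.
- SD factor: √(1 + d²), which is 1.03, 1.12 and 1.41 at d = 0.25, 0.5 and 1.0.
- Simulated power (n = 30, two-sided 5% paired t-test, effect 0.529 SD so that power is 80% at d = 0, 200,000 runs): 78.4%, 72.6% and 50.0%.

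The documents give no alpha, power, effect size or d, so every input here except the 15/15 allocation is an assumption. The figures show what a visit difference would cost; they do not show that the plan creates one.

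**The case for a change.** The strongest counter-argument accepts that the wash-out begins after the Day 40 visit and still finds a gap. Wear is printed as ending on Days 39 and 78, each test falls a day later, and the visit label fits testing with or without a lens. The plan fixes the hour of testing but not lens status. If lenses come off between 8 pm and midnight the evening before (an assumption), ocular-surface readings at 3 to 5 pm follow 15 to 21 lens-free hours; if lenses are worn to the visit, the gap is 0. Three sites must infer which applies, and lens status that nobody records cannot be recovered later.

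Part of this stands. The detail is absent, and a line in the site instructions would do no harm. If a coating effect on the ocular surface fades once lenses are removed, sites that test later after removal would see a smaller contrast, and step 5's additive cancellation would not fully cover that. Such dilution would pull a secondary sign towards no difference; it would not create a false benefit.

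The rest does not follow. A plan to read TBUT over the lens surface after each period already tells the sites that a lens must be on the eye for that test, at both visits. Losing all 30 pairs would require sites to start the wash-out ahead of the visit printed above it and then skip a planned measurement. The clinical tests are also completed on a form (Data Collection) that is not reproduced, and test order may be set there. The absence of a period term is a separate question about the analysis and gains no force from this schedule.

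**Conclusion.** The double use of Day 40 is the table's ordinary way of marking a boundary day, and it agrees with all four printed durations. The unstated lens status, hours of wear and test order are operational detail that sites following the plan can supply sensibly, because the lens-surface test itself dictates a lens on the eye and the two post-wear visits are set up identically. The realistic effect on the treated-versus-untreated comparison is nil for the questionnaires, which need no lens on the eye, and small for the secondary signs. Lens-surface TBUT is one of five such signs.

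This rests on three assumptions: the wash-out starts after the Day 40 visit, as the layout implies; each site handles Days 40 and 79 in the same way; and participants stay at one site. The Day 9 baseline, which follows a lens-free week, raises the same question about lens-dependent tests but has no bearing on the comparison, since the analysis uses no baseline value. I take no position on when lenses should be worn or removed. No change to the plan is called for.
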